Patient preferences for second-line Type 2 diabetes medication treatment outcomes

NCT05214573

22July2021

IRB Minimal Risk Protocol Template

Note: If this study establishes a human specimen repository (biobank) for research purposes, do not use this template. Use the Mayo Clinic Human Specimen Repository Protocol Template found on the IRB home page under Forms and Procedures at <http://intranet.mayo.edu/charlie/irb/>

First-time Use: Use this template to describe your study for a new IRB submission.

1. Complete the questions that apply to your study.
2. Save an electronic copy of this protocol for future revisions.
3. When completing your IRBe application, you will be asked to upload this document to the protocol section.

Modification: To modify this document after your study has been approved:

1. Open your study in IRBe. Click on the study 'Documents' tab and select the most recent version of the protocol. Save it to your files.
2. Open the saved document and activate "Track Changes".
3. Revise the protocol template to reflect the modification points, save the template to your files
4. Create an IRBe Modification for the study and upload the revised protocol template.

General Study Information

Principal Investigator: [name].

Study Title: Patient preferences for second-line Type 2 diabetes medication treatment outcomes

Protocol version number and date: Version 1; July 22, 2021

Research Question and Aims

Hypothesis: Patients with type 2 diabetes will have different preferences and priorities for what outcomes of diabetes management are most important to them.

Aims, purpose, or objectives: This study is a component of a broader study examining the comparative effectiveness and safety of second-line glucose-lowering medications in the management of type 2 diabetes. All other components of this study (other than this one) use de-identified administrative claims data from OptumLabs Data Warehouse (OLDW) and as such are exempt from IRB review.

For this human subjects study, we will elicit patient preferences toward various treatment outcomes using a participatory ranking exercise and use these rankings to generate individually weighted composite outcomes. These composite outcomes (without any linked participant information) will be used for analyses within OLDW that will estimate patient-centered treatment effects of four different classes of second-line medications for Type 2 diabetes with respect to those composite outcomes specifically. The four drug classes that will be examined

are the GLP-1 receptor agonists (GLP-1RA), SGLT2 inhibitors (SGLT2i), DPP-4 inhibitors (DPP-4i), and sulfonylureas (SU).

Background (Include relevant experience, gaps in current knowledge, preliminary data, etc.):

Type 2 diabetes (T2D) is one of the most common and serious chronic health conditions in the U.S.¹ Optimal patient-centered T2D care is predicated on treating each patient with medications that are likely to yield the most benefit and risk the least harm, weighing the best available evidence against each patient's preferences and situation. While metformin is consistently recommended as the 1st-line drug in the management of T2D, there is less clarity regarding 2nd-line therapy as new drug classes were approved and introduced into practice,²⁻⁵ resulting in decisional dilemmas for patients and clinicians, and potential missed opportunities to select the drug that best optimizes the patient's health.

Cardiovascular disease (CVD), heart failure (HF), and chronic kidney disease (CKD) are leading causes of morbidity, mortality, and costs associated with T2D.⁶⁻⁹ Randomized controlled trials (RCTs) designed to evaluate the CV safety of T2D drugs revealed additional therapeutic benefits of glucagon-like peptide-1 receptor agonists (GLP-1RA) and sodium-glucose cotransporter 2 inhibitors (SGLT2i) with respect to CVD, HF, and CKD outcomes among patients at high risk for these events. However, it is unknown how each patient's preferences and values impact the comparative effectiveness of these drugs.

As a result, patients and clinicians face a decisional dilemma at the heart of T2D management: *Which drug class would be best for the specific set of outcomes desired by an individual patient with T2D?* Addressing these knowledge gaps is critical for patients and clinicians to engage in shared decision-making; for professional societies to develop guidelines that reflect scientific evidence and patient priorities; and for health systems and payers to make formulary decisions.

Study Design and Methods

Methods: Describe in lay terms, completely detailing the research activities that will be conducted by Mayo Clinic staff under this protocol.

We will ask a purposive sample of patients with T2D (N=25) to engage in a participatory ranking exercise in which they will rank the outcomes of T2D therapy are most important to them personally and then contextualize these decisions. Participatory ranking exercises are widely used in studies of preference elicitation to determine the relative importance of treatment attributes and outcomes.¹⁰ We will develop an inventory of potential outcomes and adverse events associated with the four drug classes of interest (e.g., hospitalization, severe hypoglycemia). As part of an individual interview with a member of the research team, we will ask patient participants to rank these pre-specified outcomes in order of their relative personal importance using a secure online survey platform (Qualtrics). The researcher will ask patients to contextualize their ranking decisions. Next, participants will be asked to identify additional outcomes that are missing from this prespecified list of clinical outcomes, but which may be important to patients with T2D (e.g., medication cost, frequency of administration). Finally, participants will be asked to incorporate these additional, patient-generated outcomes into their ranking decisions and explain their rationale to the researcher.

We will seek to minimize cognitive burden on participants through iterative feedback and pilot-testing with patient-investigators, using lay language and avoiding medical jargon, identifying an appropriate number of pre-specified outcomes for ranking, and ensuring usability of Qualtrics, a secure online ranking platform. The ranking exercise will be conducted using telephone or videoconferencing software, or in person, depending on patient preference. The ranking exercise will be audio-recorded to ensure an accurate record of participant responses to questions about their ranking choices.

Subsequent to the participatory ranking exercise, all participants will be interviewed using a semi-structured interview guide. The interview guide will ask participants about their previous experiences with diabetes medications, the factors that are most important to them in general when making health care treatment decisions, the types of discussions about treatment options that occur during clinical visits, and any differences they have observed in outcomes that are important to health care providers versus those that are most important to patients.

Patient participants (N=25) will be recruited from primary care and endocrinology practices in Mayo Clinic and Mayo Clinic Health System in Minnesota and Wisconsin. Inclusion criteria are: ≥ 21 years old, T2D, use of ≥ 1 study drug (GLP-1RA, SGLT2i, DPP-4i, SU). Exclusion criteria are: insulin use, cognitive impairment, terminal/advanced illness, non-English speaking, residency in a long-term care setting.

A study coordinator at Mayo Clinic will recruit patients using Epic to identify patients who meet eligibility and sampling criteria. The study coordinator will call eligible participants to describe the study, obtain verbal informed consent, obtain HIPAA authorization, schedule the ranking exercise session, and obtain mailing information for the remuneration, which will be mailed after completion of the ranking exercise. Sampling will be guided by the principle of response saturation. We will use stratified purposeful sampling to intentionally select participants representing predefined demographic (age, sex, race/ethnicity, insurance type) and clinical (HbA_{1c} level, T2D drugs used) characteristics.

Study participation will be voluntary, and participants will be compensated with a \$25 gift card for taking part in this study.

Subject Information

Target accrual is the proposed total number of subjects to be included in this study at Mayo Clinic. A “Subject” may include medical records, images, or specimens generated at Mayo Clinic and/or received from external sources.

Target accrual: 25

Subject population (children, adults, groups): Adults with Type 2 diabetes receiving care from primary care and endocrinology practices in Mayo Clinic and Mayo Clinic Health System in Minnesota and Wisconsin.

Inclusion Criteria: ≥ 21 years old, T2D diagnosis, use of ≥ 1 study drug (GLP-1RA, SGLT2i, DPP-4i, SU)

Exclusion Criteria: Insulin use, cognitive impairment, terminal/advanced illness, non-English speaking, residency in a long-term care setting.

Biospecimens

Collection of blood samples. When multiple groups are involved copy and paste the appropriate section below for example repeat section b when drawing blood from children and adults with cancer.

a. **From healthy, non-pregnant, adult subjects who weigh at least 110 pounds.** For a minimal risk application, the amount of blood drawn from these subjects may not exceed 550ml in an 8 week period and collection may not occur more frequently than 2 times per week.

Volume per blood draw: _____ ml

Frequency of blood draw (e.g. single draw, time(s) per week, per year, etc.) _____

b. **From other adults and children considering age, weight, and health of subject.** For a minimal risk application, the amount of blood drawn from these subjects may not exceed the lesser of 50 ml or 3 ml per kg in an 8 week period, and collection may not occur more frequently than 2 times per week.

Volume per blood draw: _____ ml

Frequency of blood draw (e.g. single draw, time(s) per week, per year, etc.) _____

Prospective collection of biological specimens other than blood: _____

Review of medical records, images, specimens

Check all that apply (data includes medical records, images, specimens).

Only data that exists before the IRB submission date will be collected.

Date Range for Specimens and/or Review of Medical Records:

Examples: 01/01/1999 through 12/31/2015, or all records through mm/dd/yyyy.

Note: The Date Range must include the period for collection of baseline data, as well as follow-up data, if applicable.

The study involves data that exist at the time of IRB submission **and** data that will be generated after IRB submission. Include this activity in the Methods section.

Examples

- The study plans to conduct a retrospective chart review and ask subjects to complete a questionnaire.
- The study plans to include subjects previously diagnosed with a specific disease and add newly diagnosed subjects in the future.

The study will use data that have been collected under another IRB protocol. Include in the Methods section and enter the IRB number from which the research material will be obtained. *When appropriate, note when subjects have provided consent for future use of their data and/or specimens as described in this protocol.*

Enter one IRB number per line, add more lines as needed

Data Specimens Data & Specimens _____

Data Specimens Data & Specimens _____

Data Specimens Data & Specimens _____

Data Analysis

Power analyses may not be appropriate if this is a feasibility or pilot study, but end-point analysis plans are always appropriate even if only exploratory. Provide all information requested below, or provide justification if not including all of the information.

Power Statement: We anticipate 25 participants to be adequate to identify the heterogeneity of outcomes that matter to people living with T2D. Sampling will be guided by the principle of response saturation. We will use *stratified purposeful sampling* to intentionally select participants representing predefined demographic (age, sex, race/ethnicity, insurance type) and clinical (HbA_{1c} level, T2D drugs used) characteristics.^{11,12} Analysis (i.e. generation of the individually weighted composite outcome) will occur concurrent with data collection, and we anticipate reaching saturation in the variability of patient preference rankings of the various outcomes with no more than 25 participants.¹³⁻¹⁵

Data Analysis Plan:

Quantitative analysis of the participatory ranking exercise: Each participant's responses will be used to generate an individualized weighted composite outcome. We will consider a utility function that is a weighted combination of the individual endpoints specified by each participant, with weights determined by the patient's preferences as proposed in Butler et al.¹⁶ The patient's preference weights will be scaled to sum to 1, such that the patient-specific outcome will be a convex combination of the eligible outcomes. With the weighted utility function, we then define potentially counterfactual treatment effects, defined as the expected utility function under the four different treatment exposures. The optimal individual treatment rule is defined as in Qian and Murphy¹⁷ as the treatment that maximizes the expected utility function.

We will then use the composite outcomes generated using the participator ranking exercise (see above) in a study that uses de-identified data within OLDW. Specifically, we will emulate a target trial comparing the effectiveness of GLP1-RA, SGLT2i, DPP-4i, and SU classes with respect to each of these patient-specified composite outcomes. The target parameter will be the six pairwise differences in the personalized utility function between the drug classes. We provide an overview of that analysis below, though all analyses using

OLDW data have been previously deemed exempt from IRB review as all data is statistically de-identified by OptumLabs prior to being made available to researchers.

Primary analyses will be conducted under an intention-to-treat approach, modified to define “intention” as a patient having two consecutive fills of the assigned drug. All patients will continue follow-up and complete all outcome assessments until the planned conclusion of the study or end of observation in OLDW.

We will estimate multinomial propensity score models using data from 12 months prior to the index date to account for the multiple treatments.¹⁸ Predictions from the estimated propensity score model can be used for inverse probability weighting (IPW) to emulate baseline randomization. We will allow for flexible modeling strategies with controls to assess for overfitting. Our proposal is to use the super learner framework¹⁹ with a diverse set of individual prediction algorithms included in the ensemble. The super learner framework allows for flexible estimation of an ensemble predictor with the theoretical properties of cross-validation for model selection to control for overfitting. The framework has been demonstrated to outperform individual algorithms for the estimation of propensity scores.^{20,21} The distribution of the predicted propensity scores will be evaluated for evidence of violations of the positivity assumption. For moderate violations of positivity, the propensity scores will be truncated at 0.01 and 0.99 to control inflation of the standard errors. Our intention is to use the entire distribution of OLDW as our population of interest, but if more extreme positivity violations are observed, the reference population will be narrowed to a realistic treatment intervention population.

The proposed IPW weight with multinomial treatment groups is unstabilized, as our primary estimand is the population average treatment effect.²² If weights have extreme values when evaluating the distributions, then the stabilized version using the denominator proposed in Yoshida²³ for the optimal matching stabilized weights with multiple treatments will be used as a sensitivity analysis to avoid large confidence intervals for the effect estimates. The final propensity scores will then be incorporated as IPWs into a time-to-event model. If the proportional hazards assumptions hold, this will be a Cox model; otherwise, we will use Akaike Information Criteria to identify the best parametric time-to-event specification for the data. For the final model, we will report model diagnostic and performance statistics, and either hazard or time ratios with 95% confidence intervals. A single model with all treatment groups will be estimated and the omnibus test for at least one treatment group having a different cumulative incidence rate will be evaluated. If that test is statistically significant, then each pairwise comparison will be tested and pairwise effects estimated.

The targeted learning algorithm for the causal hazard rate as defined in Moore and van der Laan²⁴ will be implemented to estimate the four treatment hazard rates and the corresponding hazard ratios or time ratios, according to the model specification, will be estimated for each of the 6 pairwise comparisons between treatment groups. A single overall omnibus test for the four hazard rates being equal to each other versus at least one different will be conducted at the 0.05 significance level, with pairwise comparison p-values adjusted using the Holm closed sequential multiple testing procedure.^{25,26}

Predefined subgroup analyses for heterogeneity of treatment effects (HTE) will be evaluated for the following characteristics: sex (female vs. male), race/ethnicity (Black, Hispanic, Asian, other vs. White), and age (45-64, 65-74, ≥ 75 vs. <45 years). While there is no definitive evidence of HTE by these characteristics, the incidence of CVD and kidney disease outcomes are known to vary²⁷⁻³⁰ and may be mediated by different responses to therapeutic interventions. We will also assess for HTE as a function of different levels of underlying CVD risk, as the examined drugs may be more effective at reducing the risks of primary and secondary endpoints among patients at higher risk for these events or with certain CVD risk factors already present.^{31-35 36-39} The primary model will be used to estimate treatment effects across subgroups, with the targeted parameter for the subgroup analysis being the difference in the predicted treatment effect for each pairwise comparison between the

subgroups.⁴⁰ We will estimate multivariable effect prediction models^{41,42} to assess for HTE between the predefined subgroups by incorporating specific parameters for the statistical interaction effect between the treatment and subgroup variables.^{36,37} Propensity score weights will be used to emulate randomization according to the target trial framework. Internal cross-validation will be used to control for overfitting of the prediction model.⁴³ Adjustment for multiple testing will be done accounting for the total number of predefined HTE analyses.

A secondary analysis will be conducted under an as-treated approach, whereby patients will be censored upon discontinuation of the assigned treatment (no fills after 30 days beyond the dispensed pill count) or addition of another drug (i.e. another 2nd-line drug or insulin). To adjust for the likely informative censoring post-baseline, time-dependent propensity score models will be estimated and applied to dynamically reweight the population and account for time-varying confounding and informative loss to follow-up. The time-dependent propensity score models will be based on all prior covariate information up to that time point. This will address two concerns with use of observational methods for comparative effectiveness, immortal time bias⁴⁴ and time-lag bias,⁴⁵ as we will allow for time-dependent exposures and reweighting on time-conditional propensity scores.⁴⁶

Qualitative analysis of the accompanying interview: Interviews will be transcribed and analyzed according to a general thematic analysis approach (Braun & Clark, 2012) to identify patterns of meaning across patient interviews.

REFERENCES

1. CDC. National Diabetes Statistics Report, 2020. In. Atlanta, Georgia, U.S.A.: U.S. Department of Health and Human Services, Centers for Disease Control and Prevention; 2020.
2. American Diabetes Association Standards of Medical Care in Diabetes—2020. Section 9. Pharmacologic Approaches to Glycemic Treatment. *Diabetes Care*. 2020;43(Supplement 1):S98-S110.
3. NICE. National Institute for Health and Care Excellence Pathways: Managing Blood Glucose in Adults with Type 2 Diabetes. National Institute for Health and Care Excellence. <https://pathways.nice.org.uk/pathways/type-2-diabetes-in-adults>. Published 2019. Updated March 26, 2019. Accessed April 23, 2019.

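### Does the plan need a written rank-to-weight rule, and a test of it, before patient rankings can be used as utility weights?

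*Combined protocol and SAP*

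**What the plan says.** Research Question and Aims says the study will elicit preferences by a ranking exercise and "use these rankings to generate individually weighted composite outcomes". Under Study Design and Methods, participants "rank these pre-specified outcomes in order of their relative personal importance" in an online survey tool during an interview. They then add outcomes of their own and fold these into the ranking. No rating, point-allocation or trade-off task is described.

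The Data Analysis Plan, in its paragraph on the quantitative analysis of the ranking exercise, defines a utility that combines the endpoints "with weights determined by the patient's preferences as proposed in" a cited methods paper. It adds that the "preference weights will be scaled to sum to 1, such that the patient-specific outcome will be a convex combination of the eligible outcomes". The best treatment is defined "as the treatment that maximizes the expected utility function". For the claims-data (OLDW) study, "The target parameter will be the six pairwise differences in the personalized utility function between the drug classes". The plan describes its account of that study as an overview.

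The one analysis labelled a sensitivity analysis concerns stabilized propensity weights, which "will be used as a sensitivity analysis to avoid large confidence intervals for the effect estimates". Effects are also to be reported on a ratio scale: "the corresponding hazard ratios or time ratios, according to the model specification, will be estimated for each of the 6 pairwise comparisons".

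**The concern.** A ranking says which outcome comes first, not by how much. Scaling to sum to 1 normalizes weights that already exist; it does not derive them from ranks. With K outcomes, order plus sum-to-1 allows any top weight from 1/K to 1. One ranking is therefore compatible with different utility differences and sometimes with a different best class.

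If the conversion is left open, part of each participant's result comes from the analyst's choice of spacing, and a reader cannot separate that part from the stated preference. The rule could also be picked after the class comparisons have been seen. The paragraph on weights comes before the overview caveat, and the Power Statement treats generation of the composite as this study's own analysis. The missing formula is therefore not fully excused by the claims study being a separate project.

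**Working it through.** **The plan's own figure.** Four classes give 4 × 3 / 2 = 6 pairs, as stated. The sample size of 25 rests on saturation and plays no part here.

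**How far the rules differ.** K is not stated, so it is assumed. The three common rules, for rank i of K, are:
- rank-sum: 2(K + 1 − i) / [K(K + 1)]
- reciprocal: (1/i) / Σ(1/j), j = 1 to K
- rank-order-centroid: (1/K) Σ(1/j), j = i to K

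Weight on the top-ranked outcome:

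| K | rank-sum | reciprocal | centroid |
|---|---|---|---|
| 4 | 0.40 | 0.48 | 0.52 |
| 5 | 0.33 | 0.44 | 0.46 |
| 8 | 0.22 | 0.37 | 0.34 |
| 10 | 0.18 | 0.34 | 0.29 |

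**A flip is possible.** Take five outcomes in rank order with assumed risks (%): class P 4.0, 6.4, 8.4, 10.4, 12.4; class Q 5.0, 5.8, 7.8, 9.8, 11.8. Lower weighted risk is better.
- Rank-sum: P = (5×4.0 + 4×6.4 + 3×8.4 + 2×10.4 + 12.4)/15 = 104/15 = 6.933. Q = (5×5.0 + 4×5.8 + 3×7.8 + 2×9.8 + 11.8)/15 = 103/15 = 6.867. Q is better by 0.07.
- Centroid (0.457, 0.257, 0.157, 0.090, 0.040): P = 6.217, Q = 6.348. P is better by 0.13.

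The best class changes, but both gaps are small.

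**How often, under assumptions.** Inputs, all assumed: four classes; K = 6, 8 or 10; risks uniform on 1-15%; class effects with log-SD 0.2; correlation ρ of class effects across outcomes of 0, 0.5 or 0.8; 40,000 simulated risk tables per cell. Ranges run over K, and losses are in percentage points of weighted risk.

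| Across the three rules | ρ = 0 | ρ = 0.5 | ρ = 0.8 |
|---|---|---|---|
| Median movement of a difference, relative to its centroid value | 35-46% | 19-21% | 13-14% |
| A given difference changes sign | 9.8-12.9% | 4.8-5.4% | 2.6-3.0% |
| At least one of six changes sign | 45.6-54.7% | 25.1-28.2% | 14.7-16.4% |
| Best class differs | 17.3-22.5% | 8.5-9.9% | 4.7-5.4% |
| Loss above 0.5 points | 2.1-4.5% | 0.3-1.0% | 0.0-0.1% |
| Median loss when rules disagree | 0.25-0.29 | 0.18-0.21 | 0.12-0.13 |
| Mean best-to-worst spread | 1.46-1.77 | 2.59-2.68 | 3.07-3.10 |

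Disagreement rates barely move with log-SD 0.1 to 0.4 or with log-uniform risks. Losses do grow: at log-SD 0.4 the share above 0.5 points is 3.3-12.2%, 0.8-3.7% and 0.1-0.7%.

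**What a bounding analysis would return.** One possible check evaluates the limiting rank-consistent weights: equal weight on the top 1, top 2, and so on to the top K outcomes. Under the same inputs, the best class is not constant over those K points in 77-86% (ρ = 0), 52-56% (ρ = 0.5) and 32-35% (ρ = 0.8) of cases. In 60-64%, 43-46% and 27-30% of cases all three ordinary rules agree on the best class and the bounds still call it undetermined. The extremes ignore everything but one outcome, or treat a stated ranking as a complete tie.

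**Cost on the ratio scale.** Weights are specific to each participant. Covering hazard or time ratios with the K bounding points plus one alternative rule, at K = 8, would take 25 × (8 + 1) = 225 refits. The simulation averages fixed-time risks linearly and says nothing about those ratios.

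**Outcomes that cannot be measured in claims data.** Suppose the second-ranked of 10 outcomes is dropped, with centroid weights. Converting first and then rescaling gives a top weight of 0.2929/(1 − 0.1929) = 36.3%. Dropping first gives 31.4%, the centroid top weight for 9 outcomes. The order of steps matters moderately. The plan limits the composite to eligible outcomes without giving that order.

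**The case for a change.** The strongest case for a change is that the plan's target parameter and its motivating question, which class suits an individual patient, both need weights, and generating the composite belongs to this protocol. Even if the cited paper supplies a rule, no analysis described here varies it: the sensitivity analysis alters propensity weights, the subgroup analyses concern patient characteristics, and the as-treated analysis alters censoring. Utility differences move by 13-46% of their value without any change of best class. A single alternative rule would cost little on the linear scale and add no patient burden. The study's own premise, that the best class depends on what a patient values, also argues against correlations near 1, where the rule matters least.

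The reading of the text stands in full: the step is not written out and no described analysis tests it. Less of the inference stands. The cited method and the survey tool cannot be seen here, so it is not shown that a rule is absent or unsuitable. Silence about a further sensitivity analysis carries little weight in what the plan itself calls an overview of a separate, IRB-exempt study.

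**Conclusion.** No change to the plan follows. This is a gap in reporting detail, not a demonstrated error: a source and a normalization are named, no stated rule or figure is shown to be wrong, and no weight can be computed until the analyst has fixed the conversion and the handling of unmeasured outcomes. The hypothesis that patients' priorities differ does not depend on the conversion.

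A sensitivity analysis over weighting rules would be a reasonable extra, but it would not alter the primary result. The wider bounding version is a doubtful trade, since under the assumed inputs it leaves the best class undetermined in about 32-86% of cases, many of them where ordinary rules agree.

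The size is conditional throughout. Rules disagree on the best class in roughly 5-23% of simulated cases, depending mainly on an unknown correlation, and mostly in near-ties. These figures rest on assumed K, risks and effect sizes and cover only the linear utility differences. The frequency in this study is unknown.

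### The target is a utility difference that is linear in the outcomes, but class effects are planned only for the participants' own composites and reported as ratios, so they do not extend to patients with other weights

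*Combined protocol and SAP*

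**What the plan says.** All references are to the combined protocol and SAP.

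- **Background** ends on the motivating question: "Which drug class would be best for the specific set of outcomes desired by an individual patient with T2D".
- **Research Question and Aims** is narrower. The claims analysis in OLDW is to estimate effects of the four classes "with respect to those composite outcomes specifically".
- **Data Analysis Plan, quantitative analysis.** "Each participant's responses will be used to generate an individualized weighted composite outcome". The weights are normalised to total 1, so that "the patient-specific outcome will be a convex combination of the eligible outcomes". Treatment effects are "defined as the expected utility function under the four different treatment exposures", and the target parameter is the six between-class differences in utility. The emulated trial compares the classes "with respect to each of these patient-specified composite outcomes".
- **Data Analysis Plan, modelling paragraphs.** Propensity weights enter a time-to-event model: Cox if hazards are proportional, otherwise a parametric model chosen by AIC. A targeted-learning step follows. Results are reported as hazard or time ratios.
- **Power Statement.** Accrual is 25, and "we anticipate reaching saturation in the variability of patient preference rankings of the various outcomes with no more than 25 participants".

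No section plans class effects for the individual outcomes, a covariance between them, or a rule for weights other than those elicited.

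**The concern.** The plan defines a utility with a very convenient structure and then does not use it. Because the composite is a weighted sum, its expectation under a class needs only that class's expectation for each component. Those quantities do not depend on anyone's weights, so one set of estimates would serve every participant and every later patient who weights the same outcomes.

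Instead, effects are specified composite by composite, on a scale where this structure is lost. A clinician whose patient has different weights would have no planned result to use. Also, if the choice between Cox and a parametric model is made for each composite, some participants' results could be hazard ratios and others time ratios, although all rest on the same component events. At stake is whether the study delivers its own target parameter, and whether its results reach beyond the people interviewed.

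**Working it through.** **Inputs from the documents:** 4 classes; at most 25 participants with one composite each; weights summing to 1; six pairwise differences as target; ratios as reported effects. **Not given, so assumed below:** the number of outcomes K, the rule turning ranks into weights, the component effects and the event rates.

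**1. Counts.** Pairs of classes: 4 × 3 / 2 = 6, which reproduces the plan's six. Over 25 composites: 25 × 6 = 150 contrasts. The figure of 25 rests on saturation, with no formula to reproduce.

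**2. Linearity.** With U_w = Σ w_k Y_k, the expected utility under class a is E[U_w(a)] = Σ w_k E[Y_k(a)]. For classes a and b, let d_k be the difference in the expectation of outcome k and V the K × K covariance of the estimated d. The utility difference is Σ w_k d_k, with variance w'Vw. A table of 4 × K expectations with its covariance therefore gives every participant's six differences, and those for any other w on the same outcomes. At K = 8 this is 6 × 8 = 48 component contrasts.

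**3. Ratios do not have this property.** Take two components with assumed yearly rates 0.02 and 0.05 under class A, and 0.014 and 0.06 under class B.

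- Component hazard ratios (B to A): 0.014/0.02 = 0.70 and 0.06/0.05 = 1.20.
- First-event hazard ratio: 0.074/0.070 = 1.06, whatever the weights.
- Weighted means of the component ratios: 0.95 at weights 0.5/0.5 and 0.75 at 0.9/0.1. Neither equals 1.06.
- Three-year risks, 1 − exp(−3 × rate): A 0.0582 and 0.1393; B 0.0411 and 0.1647. Differences A − B: +0.0171 and −0.0254.
- Utility difference (positive favours B): 0.5 × 0.0171 − 0.5 × 0.0254 = −0.004; 0.9 × 0.0171 − 0.1 × 0.0254 = +0.013.

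The preferred class changes where the first weight is 0.0254/(0.0171 + 0.0254) = 0.60. The first-event ratio cannot show this. The plan does not say how a weighted composite becomes an event time, so the first-event form is an illustration.

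**4. Can other weights be reached from the 25?** On the utility scale, often yes. With 25 random rank-sum weight vectors on a common set of outcomes, the weight matrix had full rank K in all 100 simulations at each K tried from 5 to 25, and a new patient's contrasts were recovered to within rounding. Recovery failed at K = 26 and 30, where the rank is only 25. The new vector lay inside the convex hull of the 25 in 15% of simulations at K = 5 and in none at K of 8 or more. Recovery is thus mostly extrapolation, and its interval needs a joint covariance between composites that the plan does not mention.

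**5. How close would the 25 be?** At most 25/K! of full rank orders are covered: all 24 at K = 4, 20.8% at K = 5, 3.5% at K = 6, 0.06% at K = 8. If a new patient simply borrowed the nearest composite, the best class differed in 11% (K = 5), 19% (K = 8) and 22% (K = 10) of simulated patients. Those runs assumed uniform rank orders, rank-sum weights and independent component effects. Other assumed weight rules and degrees of agreement between patients, at K = 6 to 10, gave 8% to 27%.

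**The case against.** A reader might infer that the plan cannot answer its question for anyone outside the 25. The documents do not support that. By the linearity in step 2, utility differences for 25 full-rank weight vectors on a common set of at most 25 outcomes determine the point estimate for other weights. What is missing is provision for this, and a scale on which it works.

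A reader might also take 8% to 27% as the share of patients who would be given the wrong class. The plan never proposes borrowing the nearest composite, and every input to that range is assumed. Near-ties count as mismatches: in a repeat of the set-up with mismatch of 8% to 26%, the mean utility lost was only about 1.5% to 9% of the gap between best and worst class.

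Three further objections carry some weight.

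- **The stated aim is narrower.** Research Question and Aims confines the claims analysis to the participants' composites, and sampling to saturation is the intended bridge to other patients. This is fair, so the shortfall is against the motivating question in Background. But saturation concerns the variety of rankings and supplies no treatment effect for an unsampled weight vector.
- **Component effects may be estimated elsewhere.** The study is part of a broader programme, and the claims analysis is presented as an overview. The documents neither show nor exclude this. If they are, a cross-reference plus the covariance would do.
- **Participants may add outcomes.** The component set can then differ between people, and some additions may not appear in claims. This limits the remedy, but it limits the planned composites equally.

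**Conclusion.** The point holds as an omission and a mismatch of scale. The plan targets differences in an expected utility that is linear in its components, but specifies effects only for at most 25 composites and reports ratios that are not linear in them. As written, it makes no provision for patients with other weights, and its reported ratios cannot be carried over to them. The algebra in step 2 needs only the plan's own definition of the composite. The numerical example and the mismatch rates rest on assumed rates, K, weights and effects, and show direction rather than size. At very small K the coverage problem largely disappears, while the scale mismatch remains. This is an inexpensive improvement worth making before the claims analysis, and does not invalidate the ranking study.

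**What to change.** In the quantitative part of the Data Analysis Plan:

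1. For each eligible outcome measurable in claims, pre-specify the class-specific mean, or risk at a fixed horizon, estimated by the planned weighting or targeted-learning methods: 4 classes by K outcomes, with the joint covariance across outcomes and classes.
2. Compute each participant's six utility differences as weighted sums, with variance w'Vw.
3. Report the 4-by-K table and its covariance, so that the best class and its uncertainty can be computed for any weights on those outcomes.

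Match the modelling paragraphs to this, so that the primary report and its tests are on the utility-difference scale. Hazard or time ratios can stay as supplementary results.

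The cost is some added analysis, a horizon that must be chosen and justified in advance, and wording changes. No new participants are needed. Participant-added outcomes that claims do not record would remain uncovered, and the report should list them.
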